9.4.4 Pulse Oximetry

For the on-treatment pulse oximetry measurements taken at each CPET before the start of any exercise, a summary of raw values and change from baseline values will be provided by treatment groups at each scheduled time point for the percent of oxygen saturation by pulse oximetry. In addition, the mean value at each visit will be plotted by treatment groups for the percent of oxygen saturation.

9.4.5 Physical Examination

PE findings, which are only collected at Screening in the database, will be presented as a data listing only.

9.4.6 Ophthalmologic Examination

Abnormal ophthalmologic examination findings will be presented as a data listing only.

9.5 Narratives Listings

Narratives listings will be provided for subjects with any of the following events that occurred by the study cutoff date:

- Death
- Serious TEAEs
- TEAEs leading to treatment discontinuation
- TEAEs leading to treatment interruption
- Pregnancy

10 INTERIM AND DMC ANALYSES

10.1 Interim Analysis

No interim analysis is planned.

10.2 DMC Analysis

No DMC analysis is planned

12 APPENDICES

Appendix A Schedule of Assessments

Table 12-1 Study VX15-809-112: Treatment Period and Safety Follow-up Visit

Event/Assessment	Treatment Period			Early Termination of Treatment ^a	Safety Follow-up 4 Weeks (± 7 Days) After Last Dose ^a
	Day 1	Week 12 (± 7 Days)	Week 24 (± 7 Days)		
Clinic Visit	X	X	X	X	X
Randomization	X				
CFQ-R, PHQ-8, and GAD-7 ^b	X	X	X	X	
Height and weight ^c	X	X	X	X	X
Vital signs ^d	X	X	X	X	X
Spirometry ^e	X	X	X	X	
Physical examination (PE) ^f	X				X
Ophthalmologic examination			X ^g	X ^g	X ^g
Cardiopulmonary exercise test (CPET) ^h	X	X	X	X	
Urine β-HCG ⁱ	X	X	X	X	X
Serum chemistry ^j	X	X	X	X	X
Hematology ^j	X	X	X	X	X

^a If the subject prematurely discontinues study drug, an Early Termination of Treatment (ETT) Visit should be scheduled as soon as possible after the subject decides to discontinue. If the ETT Visit occurs 3 weeks after the last dose of study drug or later, then the ETT Visit will replace the Safety Follow-up Visit, and a separate Safety Follow-up Visit will not be required. When the Safety Follow-up Visit is complete, the subject has completed the study.

^b All questionnaires must be completed before the start of any other assessments scheduled at that visit. The CFQ-R must be completed first, then the PHQ-8 and GAD-7.

^c During the Treatment Period and at the Safety Follow-up Visit, height will be collected only for subjects who were 21 years of age or younger at the Screening Visit. Height and weight will be measured with shoes off.

^d Vital signs (systolic and diastolic blood pressure, oral temperature, pulse rate, and respiration rate) will be collected before study drug dosing and after the subject has been seated for at least 5 minutes. Blood pressure will be taken using a manual sphygmomanometer.

^e Spirometry will be assessed before CPET.

^f The physical examination includes an assessment of all body systems. Symptom-directed physical examinations will occur at any time during the study if triggered by AEs or if deemed necessary by the investigator.

^g For all subjects <18 years of age at the Screening Visit, except for those who have had bilateral lens removal, an ophthalmologic examination will be conducted by a licensed ophthalmologist or optometrist at 1 of the following visits: the Week 24 Visit, the ETT Visit, or the Safety Follow-up Visit.

^h CPET includes pulse oximetry.

ⁱ Pregnancy tests will be performed for all female subjects of childbearing potential. A urine β-hCG test will be performed on Day 1 (before first dose of study drug) and every 4 weeks thereafter. When there is not a scheduled study visit, the pregnancy test will be conducted with a urine home pregnancy test kit provided by the study site. For tests performed at home, the site staff will telephone the subject to confirm the test results.

^j On Day 1, blood samples for chemistry and hematology tests will be collected before the first dose of study drug. At other scheduled visits, these samples may be collected at any time during the visit.

Table 12-1 Study VX15-809-112: Treatment Period and Safety Follow-up Visit

Event/Assessment	Treatment Period			Early Termination of Treatment ^a	Safety Follow-up 4 Weeks (± 7 Days) After Last Dose ^a
	Day 1	Week 12 (± 7 Days)	Week 24 (± 7 Days)		
Study drug dispensed ^k	X	X			
Study drug dosing	LUM 400 mg/IVA 250 mg q12h or placebo q12h				
Study drug count		X	X	X	
Reminder of standard exercise recommendations ^l	X	X			
Activity and sleep tracking via actigraphy	Continuous from Day 1 through Week 24 Visit				
Recording concomitant medications and treatments/procedures	Continuous from signing of ICF through Safety Follow-up Visit				
Recording AEs	Continuous from signing of ICF through Safety Follow-up Visit				

^k Study drug will be administered orally, 2 times a day, within 30 minutes of consumption of fat-containing food.
^l

Appendix B Precisions of Summary for Continuous Variables

Continuous Variables

Table 12-2 Precision of Special Summary Statistics for CF Studies

Variables	Statistics	Decimal Places
CPET Related variables	Mean, LS mean, 95% CI	1
Percent Predicted FEV ₁	Mean, LS mean, 95% CI	1
CFQ-R	Mean, LS mean, 95% CI	1
BMI	Mean, LS mean, 95% CI	1
PHQ-8/GAD-7	Mean, 95% CI	1
Demographics	Mean, 95% CI	1
Actigraphy	Mean, 95% CI	1

The precision of the Safety Lab Data will follow the latest standard from the Biometrics Standardization Committee.

The precision of the measurement in raw data for other continuous variables will be used to determine the number of decimal places to present in tables, figures, and derived listings. Minimum and maximum values will be reported with the same precision as the units of measure. The mean and median will be reported to 1 greater decimal place, and the SD and SE will be reported to 2 additional decimal places.

Any values that require transformation to standard units (metric or International System [SI]) will be converted with the appropriate corresponding precision.

Appendix C Analysis Visit Window Mapping Rules for Safety and Pharmacodynamic and Actigraphy Measurements

Table 12-3 Visit Window Mapping Rules for Safety and Pharmacodynamic and Actigraphy Measurements

Assessments	Visit	Target Study Day	Visit Window (in study days)
• CPET related	Week 12	85	(1, 92]
•	Week 24	169	[93, 176]
• Spirometry	Safety follow up week 28	197	[177, 204]
•			
• CFQ-R/PHQ-8/GAD-7			
•			
• Weight and Height			
•			
• Vital Signs			
•			
• Actigraphy*			
•			
• Labs – Liver Function Test			

* Baseline actigraphy data will be the average of the corresponding actigraphy data 7 days prior to the Day 1 visit (Day -7 to Day -1). The same rule applies to actigraphy data collected at week 12 and week 24, where the average of the corresponding actigraphy data 7 days prior to the target day visit (target study Days 85 and 169 will be used for these two visits). Due to a window of ± 7 Days for each of these visits, the actual 7-day interval from which actigraphy data is used may vary from subject to subject.

Appendix D Coefficients for Hankinson and Wang Methods for Calculating Predicted Spirometry Parameters

Percent predicted FEV₁ is the ratio of FEV₁ (L) to the predicted FEV₁ (L), expressed as a percentage. The predicted FEV₁ (L) will be calculated using the Hankinson¹ and Wang² standards.

The Hankinson standard will be applied to male subjects 18 years and older and female subjects 16 years and older; the Wang standard will be applied to male subjects 6 to 17 years and female subjects 6 to 15 years of age. During the study, the subjects who have a birthday that would move them from Wang to Hankinson will use the Wang standard before that birthday and the Hankinson standard at or after that birthday.

Hankinson Normal Values (HNVs) will be calculated for FEV₁, forced vital capacity (FVC), forced expiratory flow mid expiratory phase (FEF_{25-75%}), and FEV₁/FVC% using the Hankinson equation:

$$\text{Predicted lung function parameter} = b_0 + b_1 \times \text{age} + b_2 \times \text{age}^2 + b_3 \times \text{height}^2$$

In the equation, height is given in centimeters, age is given in years, and the coefficients b₀, b₁, b₂, and b₃ are determined based on subject's sex, race, and age group as shown in Table 12-4

Wang Normal Values (WNVs) will be calculated for FEV₁, FVC, FEF_{25-75%}, and FEV₁/FVC using the Wang equation:

$$\ln(\text{Predicted lung function parameter}) = \alpha + \beta \ln(\text{height})$$

Wang Normal Values (WNVs) will be calculated for FEV₁, FVC, FEF_{25-75%}, and FEV₁/FVC using the Wang equation. In the equation, height is given in meters, and the coefficients α and β are determined based on subject's sex, race, and age as shown in Table 12-5 and Table 12-6.

If either height or age is missing, and the spirometry measurement is non-missing, the last non-missing value of height and age will be used in the calculation of predicted values.

Table 12-4 HNVs Equation Coefficients by Sex, Race, and Age

Parameter	Sex	Race	Age (years)	b ₀	b ₁	b ₂	b ₃	
HNV _{FEV1}	Male	Caucasian	<20	-0.7453	-0.04106	0.004477	0.00014098	
			≥20	0.5536	-0.01303	-0.000172	0.00014098	
		African American	<20	-0.7048	-0.05711	0.004316	0.00013194	
			≥20	0.3411	-0.02309		0.00013194	
		Mexican American	<20	-0.8218	-0.04248	0.004291	0.00015104	
			≥20	0.6306	-0.02928		0.00015104	
		Female	Caucasian	<18	-0.8710	0.06537		0.00011496
				≥18	0.4333	-0.00361	-0.000194	0.00011496
	African American		<18	-0.9630	0.05799		0.00010846	
			≥18	0.3433	-0.01283	-0.000097	0.00010846	
	Mexican American		<18	-0.9641	0.06490		0.00012154	
			≥18	0.4529	-0.01178	-0.000113	0.00012154	
	HNV _{FVC}	Male	Caucasian	<20	-0.2584	-0.20415	0.010133	0.00018642
				≥20	-0.1933	0.00064	-0.000269	0.00018642
African American			<20	-0.4971	-0.15497	0.007701	0.00016643	
			≥20	-0.1517	-0.01821		0.00016643	
Mexican American			<20	-0.7571	-0.09520	0.006619	0.00017823	
			≥20	0.2376	-0.00891	-0.000182	0.00017823	
Female			Caucasian	<18	-1.2082	0.05916		0.00014815
				≥18	-0.3560	0.01870	-0.000382	0.00014815
		African American	<18	-0.6166	-0.04687	0.003602	0.00013606	
			≥18	-0.3039	0.00536	-0.000265	0.00013606	
		Mexican American	<18	-1.2507	0.07501		0.00014246	
			≥18	0.1210	0.00307	-0.000237	0.00014246	
HNV _{FEF25-75%}		Male	Caucasian	<20	-1.0863	0.13939		0.00010345
				≥20	2.7006	-0.04995		0.00010345
	African American		<20	-1.1627	0.12314		0.00010461	
			≥20	2.1477	-0.04238		0.00010461	
	Mexican American		<20	-1.3592	0.10529		0.00014473	
			≥20	1.7503	-0.05018		0.00014473	
	Female		Caucasian	<18	-2.5284	0.52490	-0.015309	0.00006982
				≥18	2.3670	-0.01904	-0.000200	0.00006982
		African American	<18	-2.5379	0.43755	-0.012154	0.00008572	
			≥18	2.0828	-0.03793		0.00008572	
		Mexican American	<18	-2.1825	0.42451	-0.012415	0.00009610	
			≥18	1.7456	-0.01195	-0.000291	0.00009610	
	HNV _{FEV1/FVC%}	Male	Caucasian		88.066	-0.2066		
			African American		89.239	-0.1828		
Mexican American				90.024	-0.2186			
Female		Caucasian		90.809	-0.2125			
		African American		91.655	-0.2039			
		Mexican American		92.360	-0.2248			

Source: Reference 1

Table 12-5 WNVs Equation Coefficients by Sex and Age in White Boys and Girls

Sex	Age	FEV ₁		FVC		FEF _{25-75%}		FEV ₁ /FVC	
		α	β	α	β	α	β	α	β
Male	6	-0.109	2.252	-0.024	2.470			-0.078	-0.248
	7	-0.104	2.270	-0.018	2.489			-0.086	-0.220
	8	-0.089	2.257	0.005	2.443	0.264	1.505	-0.091	-0.199
	9	-0.063	2.197	0.017	2.426	0.308	1.443	-0.086	-0.206
	10	-0.057	2.212	0.030	2.407	0.290	1.557	-0.081	-0.209
	11	-0.093	2.324	0.009	2.468	0.242	1.738	-0.101	-0.147
	12	-0.161	2.512	-0.061	2.649	0.165	1.982	-0.101	-0.133
	13	-0.292	2.843	-0.175	2.924	0.007	2.396	-0.116	-0.085
	14	-0.329	2.983	-0.219	3.060	0.014	2.483	-0.106	-0.087
	15	-0.141	2.709	-0.079	2.859	0.241	2.163	-0.060	-0.155
	16	0.062	2.409	0.104	2.591	0.503	1.764	-0.045	-0.178
17	0.262	2.099	0.253	2.374	0.762	1.368	0.008	-0.272	
Female	6	-0.109	1.949	-0.013	2.007			-0.097	-0.055
	7	-0.144	2.243	-0.062	2.385			-0.084	-0.132
	8	-0.137	2.239	-0.055	2.381	0.247	1.668	-0.079	-0.152
	9	-0.123	2.222	-0.039	2.351	0.254	1.710	-0.084	-0.128
	10	-0.161	2.364	-0.068	2.458	0.195	1.933	-0.092	-0.097
	11	-0.223	2.558	-0.120	2.617	0.161	2.091	-0.102	-0.061
	12	-0.264	2.709	-0.174	2.776	0.185	2.120	-0.090	-0.067
	13	-0.153	2.535	-0.061	2.576	0.294	1.976	-0.093	-0.040
	14	0.046	2.178	0.139	2.208	0.450	1.711	-0.096	-0.026
15	0.148	2.008	0.210	2.099	0.581	1.486	-0.062	-0.093	

Source: Reference 1

Table 12-6 WNVs Equation Coefficients by Sex and Age in Black Boys and Girls

Sex	Age	FEV ₁		FVC		FEF _{25-75%}		FEV ₁ /FVC	
		α	β	α	β	α	β	α	β
Male	6	-0.166	1.723	-0.088	1.961			-0.091	-0.152
	7	-0.122	1.846	-0.040	2.040			-0.091	-0.153
	8	-0.225	2.271	-0.094	2.323	0.097	1.544	-0.118	-0.104
	9	-0.142	2.059	-0.074	2.308	0.255	1.248	-0.079	-0.218
	10	-0.157	2.117	-0.110	2.417	0.230	1.428	-0.047	-0.303
	11	-0.176	2.166	-0.138	2.453	0.256	1.438	-0.048	-0.263
	12	-0.307	2.548	-0.224	2.710	0.085	1.936	-0.084	-0.162
	13	-0.486	2.962	-0.342	2.975	-0.121	2.476	-0.141	-0.018
	14	-0.472	3.010	-0.337	3.035	-0.115	2.536	-0.123	-0.050
	15	-0.318	2.789	-0.226	2.889	0.170	2.120	-0.070	-0.140
	16	0.074	2.140	0.058	2.425	0.663	1.299	0.018	-0.289
17	0.053	2.223	0.148	2.310	0.505	1.618	-0.095	-0.087	
Female	6	-0.288	2.182	-0.172	2.117			-0.109	0.059
	7	-0.250	2.158	-0.135	2.132			-0.104	-0.030
	8	-0.276	2.295	-0.176	2.362	-0.283	2.990	-0.103	-0.066
	9	-0.294	2.330	-0.200	2.452	0.025	2.062	-0.097	-0.104
	10	-0.344	2.507	-0.230	2.571	0.051	2.028	-0.120	-0.043
	11	-0.308	2.460	-0.204	2.526	0.078	2.006	-0.089	-0.105
	12	-0.219	2.312	-0.107	2.342	0.225	1.804	-0.115	-0.021
	13	-0.117	2.196	-0.042	2.294	0.418	1.504	-0.051	-0.148
	14	0.041	1.920	0.105	2.021	0.574	1.257	-0.063	-0.103
15	0.203	1.662	0.253	1.787	0.599	1.281	-0.043	-0.139	

Source: Reference 2 (Tables 4 and 5)

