Table 3-2 Study VX15-809-112: Treatment Period and Safety Follow-up Visit

Event/Assessment	Treatment Period			Early Termination of Treatment ^a	Safety Follow-up 4 Weeks (± 7 Days) After Last Dose ^a
	Day 1	Week 12 (± 7 Days)	Week 24 (± 7 Days)		
Clinic Visit	X	X	X	X	X
Randomization	X				
CFQ-R, PHQ-8, and GAD-7 ^b	X	X	X	X	
Height and weight ^c	X	X	X	X	X
Vital signs ^d	X	X	X	X	X
Spirometry ^e	X	X	X	X	
Physical examination (PE) ^f	X				X
Ophthalmologic examination			X ^g	X ^g	X ^g
Cardiopulmonary exercise test (CPET) ^h	X	X	X	X	
Urine β-HCG ⁱ	X	X	X	X	X
Serum chemistry ^j	X	X	X	X	X
Hematology ^j	X	X	X	X	X

^a If the subject prematurely discontinues study drug, an Early Termination of Treatment (ETT) Visit should be scheduled as soon as possible after the subject decides to discontinue. If the ETT Visit occurs 3 weeks after the last dose of study drug or later, then the ETT Visit will replace the Safety Follow-up Visit, and a separate Safety Follow-up Visit will not be required. When the Safety Follow-up Visit is complete, the subject has completed the study.

^b All questionnaires must be completed before the start of any other assessments scheduled at that visit. The CFQ-R must be completed first, then the PHQ-8 and GAD-7.

^c During the Treatment Period and at the Safety Follow-up Visit, height will be collected only for subjects who were 21 years of age or younger at the Screening Visit. Height and weight will be measured with shoes off.

^d Vital signs (systolic and diastolic blood pressure, oral temperature, pulse rate, and respiration rate) will be collected before study drug dosing and after the subject has been seated for at least 5 minutes. Blood pressure will be taken using a manual sphygmomanometer.

^e Spirometry will be assessed before the CPET.

^f The physical examination includes an assessment of all body systems. Symptom-directed physical examinations will occur at any time during the study if triggered by AEs or if deemed necessary by the investigator.

^g For all subjects <18 years of age at the Screening Visit, except for those who have had bilateral lens removal, an ophthalmologic examination will be conducted by a licensed ophthalmologist or optometrist at 1 of the following visits: the Week 24 Visit, the ETT Visit, or the Safety Follow-up Visit.

^h The CPET includes pulse oximetry.

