8.1.4 Early Termination of Treatment

If the subject prematurely discontinues study drug, an Early Termination of Treatment (ETT) Visit will be scheduled as soon as possible after the subject decides to terminate study drug. Subjects who prematurely discontinue study drug will also complete the Safety Follow-up Visit, approximately 4 weeks ± 7 days after their last dose of study drug. The assessments performed at the Safety Follow-up Visit are listed in [Table 3-2](#).

If the ETT Visit occurs 3 weeks after the last dose of study drug or later, then the ETT Visit will replace the Safety Follow-up Visit, and a separate Safety Follow-up Visit will not be required.

If the subject withdraws consent for the study, no further evaluations will be performed, and no additional data will be collected. Vertex Pharmaceuticals Incorporated (Vertex) may retain and continue to use any data collected before such withdrawal of consent.

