10.2 Administration

Study drug will be administered orally, 2 times a day, with food. Study drug should be administered within 30 minutes of consuming fat-containing food such as a standard CF high-fat, high-calorie meal or snack according to the following guidelines:

1. Study drug will be administered q12h (\pm 2 hours).
2. On days of scheduled visits, the morning dose of study drug will be administered at the site after predose assessments have been completed. The meal or snack will be provided by the site for the morning dose of study drug.
3. If a subject's scheduled visit is to occur in the afternoon, the following guidelines must be used:
 - If the dose in the clinic will be within 6 hours of the subject's scheduled morning dose, the subject should withhold their morning dose of study drug and the morning dose will be administered in the clinic.
 - If the dose in the clinic will be more than 6 hours after the subject's scheduled morning dose, the subject should take the morning dose at home and the evening dose will be administered in the clinic. In this event, all assessments will be collected relative to the evening dose.
4. For visits after the Day 1 Visit, subjects will be instructed to bring all used and unused study drug to the site; study drug will be dispensed at each visit, as appropriate.
5. At the Week 24 Visit, the morning dose of study drug will NOT be administered. The last dose of study drug will be the evening dose administered the day before the Week 24 Visit.

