7.2 Sample Size and Power

Assuming a common standard deviation (SD) of 10% for the primary efficacy endpoint and a dropout rate of 10%, a sample size of 33 subjects in each treatment group would provide at least 80% power to detect a difference of 7.5% between the means for the 2 treatment groups using a 2-sided test at the 0.05 significance level. If the true difference is smaller, or if there

is greater variability, a larger sample size would be required to provide 80% power. Table 7-1 shows the required sample sizes for various assumptions about the true treatment effect using a 2-sided test at the 0.05 significance level.

Because LUM/IVA has recently been approved in several countries, additional data independent of this study may emerge while this study is underway, which would allow a more precise estimation of the true treatment effect. The final sample size may be recalculated based on these data, and the protocol may be amended as appropriate.

Table 7-1 Sample Sizes for 80% Power

True Difference Between Placebo and LUM/IVA Effects on Primary Endpoint	Sample Size Needed for 80% Power (subjects per treatment group)
5.0%	72
5.5%	59
6.0%	50
6.5%	44
7.0%	38
7.5%	33

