9 STATISTICAL ANALYSIS

9.1 General Considerations

The Schedule of Assessments is provided in Appendix A.

All individual subject data for those randomized or exposed to study drug will be presented in data listings.

Continuous variables will be summarized using the following descriptive summary statistics: the number of subjects (n), mean, standard error (SE), standard deviation (SD), median, minimum value (min), and maximum value (max). The precision of the measurement for each continuous variable will be used to determine the number of decimal places to present in tables, figures, and derived listings. Minimum and maximum values will be reported with the same precision as the units of measure. The mean and median will be reported to 1 greater decimal place, and the SE and SD will be reported to 2 additional decimal places. Any values that require transformation to standard units (metric or SI) will be converted with the appropriate corresponding precision.

Categorical variables will be summarized using counts and percentages. Percentages will be presented to 1 decimal place.

Baseline Value: Unless otherwise specified, the baseline value will be defined as the most recent non-missing measurement (scheduled or unscheduled) collected prior to the initial administration of study drug. Baseline CPET data will be collected on Day 1 prior to the initial administration of study drug. Unscheduled visit measurements will be included for derivation of baseline. For actigraphy variables, baseline data will be defined as the mean of the data collected for the 7 days immediately preceding Day 1 (Day -7 to Day -1) during the Screening Period.

Absolute Change from baseline will be calculated as Post baseline value - Baseline value.

Relative change from baseline will be calculated and expressed in percentages as $100 \times \frac{(\text{Post baseline value} - \text{Baseline value})}{\text{Baseline value}}$.

Unscheduled Visits: Unscheduled visit measurements will be included in listings, for derivation of visit windows and computation of baseline/last on-treatment visit, and for the analysis of maximum/minimum on-treatment values and maximum/minimum changes from baseline values.

Visit Windows: Appendix C defines the visit window mapping rules to derive the analysis visits.

Repeated observations within the same visits window

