- For all efficacy parameters, if there are multiple measurements within a visit window, the record at the scheduled visit will be used. If there are no measurements at the scheduled visit, then 1) the record closest to the target day will be used; or 2) if there are multiple records with the same distance to the target day, the latest record will be used.
- For all safety parameters, if there are multiple measurements within a visit window, then 1) the record closest to the target day will be used; or 2) if there are multiple records with the same distance to the target day, the latest record will be used.

BMI will follow visit window rules for efficacy parameters when being considered as an efficacy endpoint.

Incomplete/Missing data will not be imputed, unless otherwise specified; i.e., all missing values will remain as missing in all statistical analyses and listings, unless otherwise specified. Missing post-baseline values will not be imputed for efficacy analysis conducted

using a mixed model for repeated measures (MMRM) approach, which makes use of all available data even if a subject has missing data at some post-baseline visits.

Outliers: No formal statistical analyses will be performed to detect and/or remedy the presence of statistical outliers.

Repeated Observations: Measurements recorded at different time points are defined as repeated observations. If an assessment has planned repeated measurements, then statistical summaries will present all planned time points, as appropriate.

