9.3 Efficacy Analysis

Unless otherwise defined, all efficacy analyses described in this section will include all measurements up to Week 24 [inclusive], both on-treatment measurements and measurements after treatment discontinuation.

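### A Week 24 CPET done after Day 176 is mapped to safety follow-up by SAP Table 12-3 and drops out of the primary Week 24 contrast

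*SAP*

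**What the plan says.** SAP 9.1 states that "Appendix C defines the visit window mapping rules to derive the analysis visits". In Appendix C, Table 12-3 gives one set of windows for CPET, spirometry, questionnaires, weight and height, vital signs, actigraphy and liver tests:

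- Week 12: target Day 85, window after Day 1 up to Day 92.
- Week 24: target Day 169, window Days 93 to 176.
- "Safety follow up week 28": target Day 197, window Days 177 to 204.

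For efficacy parameters SAP 9.1 adds that "if there are multiple measurements within a visit window, the record at the scheduled visit will be used". SAP 9.3 says that efficacy analyses "will include all measurements up to Week 24 [inclusive], both on-treatment measurements and measurements after treatment discontinuation". SAP 9.3.1.2 makes the Week 24 treatment effect from the MMRM the primary result and imputes nothing.

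Protocol Table 3-2, repeated in SAP Appendix A, schedules CPET, spirometry and questionnaires at Day 1, Week 12, Week 24 and the Early Termination of Treatment (ETT) Visit, but not at Safety Follow-up. The exception is in Protocol 8.1.4: if the ETT Visit takes place 3 weeks or more after the last dose, "then the ETT Visit will replace the Safety Follow-up Visit".

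**The concern.** For CPET, spirometry and questionnaires, the follow-up row has no planned test of its own to receive. It can catch only a late Week 24 test, an ETT test or an unscheduled one. A subject who comes for the Week 24 visit eight days after target has a valid VO2max measurement. The table nevertheless labels it as follow-up, and the Week 24 value becomes missing. The rule for choosing between records cannot bring it back, because that rule applies only to records already inside the same window.

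The SAP expects off-schedule tests: Appendix G, item 8, lists them as important deviations. It does not say whether their values are used. At stake are observed values of the primary endpoint in a trial of about 66 subjects. If the rule is not settled first, there may also be a choice to make about individual values after unblinding.

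**Working it through.** **1. Day mapping.** Week 24 target = 24 × 7 + 1 = Day 169. The protocol allows ±7 days, so Days 162 to 176.

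| Study day | Days from target | Table 12-3 visit |
|---|---|---|
| 162 | −7 | Week 24 |
| 176 | +7 | Week 24 |
| 177 | +8 | Safety follow-up |
| 204 | +35 | Safety follow-up |
| 205 | +36 | none |

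The upper edge is exactly the protocol limit, so only a test outside the ±7 days is affected.

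**2. Could Days 177 to 181 be a completer's scheduled follow-up?** Protocol 10.2, item 5: "The last dose of study drug will be the evening dose administered the day before the Week 24 Visit". The earliest on-time Week 24 visit is Day 162, so the last dose is on Day 161. Follow-up is 28 ± 7 days after the last dose, so at the earliest 161 + 21 = Day 182. The first five days of the row cannot be an on-schedule follow-up visit of a subject who completed treatment on time.

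**3. The plan's sample size.** Inputs from SAP 7.2: SD 10, difference 7.5, two-sided 0.05, power 80%, dropout 10%. A two-sample t-test (noncentral t) needs 29 evaluable subjects per arm, and 29/0.9 = 32.2, rounded up to 33. The same method reproduces the other rows of Table 7-1 (72, 59, 50, 44, 38). The sample size is sound.

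**4. Cost of lost tests.** SE = 10 × √(2/n), where n is the number of Week 24 values per arm. The number lost, k, is an assumption (1, 3 or 6 in total, split evenly), because the documents give none. There are two bases:

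- Base A, all dropouts missing at Week 24: 33 × 0.9 = 29.7 per arm.
- Base B, every dropout has an ETT CPET, stopping times are uniform over 168 days, and those on Days 93 to 168 (76 days) count as Week 24: 29.7 + 3.3 × 76/168 = 31.19 per arm.

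| Lost in total | A: n, SE | A: power | B: n, SE | B: power |
|---|---|---|---|---|
| 0 | 29.7, 2.60 | 81.1% | 31.19, 2.53 | 83.0% |
| 1 | 29.2, 2.62 | 80.4% | 30.69, 2.55 | 82.4% |
| 3 | 28.2, 2.66 | 79.0% | 29.69, 2.60 | 81.1% |
| 6 | 26.7, 2.74 | 76.7% | 28.19, 2.66 | 79.0% |

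**5. Partial recovery through Week 12.** Assume a correlation r = 0.5 between the Week 12 and Week 24 changes, with Week 12 present for all n₀ subjects of the base. The variance is then 200 × [(1 − r²)/n + r²/n₀]. Power for 1, 3 and 6 lost tests is 80.6%, 79.5% and 77.7% on base A, and 82.5%, 81.5% and 79.9% on base B. Neither base counts any precision gained from the planned covariates.

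**The case against.** The strongest reply is that nothing done according to protocol is lost. The window ends exactly where the protocol's visit window ends, each window closes at target + 7, and the rule is fixed in advance. It applies by study day whatever the subject's treatment status. A test it drops is already a listed deviation. The follow-up row is needed for vital signs, weight and liver tests, and adjoining windows must meet somewhere. All of this stands, and it is why the point is minor. It does not explain why CPET should share a follow-up row with assessments that are collected at follow-up. Nor does it justify discarding an observed primary-endpoint value when SAP 9.3 keeps even measurements taken after treatment stopped.

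A reader might infer that a late test is certainly an on-treatment test. The documents do not establish this. Protocol 10.2 ties the last dose to the evening before the Week 24 Visit, but the plan is for 24 weeks of study drug, dispensed only at Day 1 and Week 12. Dosing beyond Day 176 is not shown.

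A reader might also conclude that any visit labelled Week 24 should simply be kept. Without a cap, that rule would admit very late tests. It would also admit a completer's test on a given day but not an ETT test on the same day, contrary to the equal treatment in SAP 9.3.

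**Conclusion.** The point holds as a minor one. As written, a Week 24 CPET on Day 177 or later is missing from the primary Week 24 contrast, and neither document has a rule that restores it. The same applies to spirometry and the questionnaires.

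The size is unknown and probably small. It is zero if no test is late. On the assumed counts, power falls by about 0.6 to 0.7 percentage points for one lost test and by about 4.0 to 4.4 points for six, before any recovery through Week 12. Whether power goes below 80% depends on the base: three lost tests do this on base A but not on base B.

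Two stronger conclusions are not supported. A reader might infer that the trial is underpowered, but the sample size reproduces and no late-test count is given. A reader might infer that the subject is lost, but only the Week 24 value is, since a Week 12 CPET still enters the MMRM and informs the Week 24 estimate under missing at random.

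**What to change.** Before unblinding:

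1. In Table 12-3, for CPET, spirometry and questionnaires only, extend the upper limit of the Week 24 window past Day 176 to one fixed, pre-specified day no later than Day 204. Apply it by study day to all subjects, whether or not they completed treatment.
2. State in SAP 9.3 that data up to and including Week 24 means data within this window.
3. Leave the follow-up row as it is for vital signs, weight and liver tests.
4. Repeat the primary analysis with the Day 176 limit as a sensitivity analysis.

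The existing SAP 9.1 rule already decides between two records in the longer window. The cost is one sentence in the table, one phrase in SAP 9.3 and one extra run, with no new data. It does change the upper edge of the primary Week 24 window. The downside is that a few tests outside the ±7-day visit window, some possibly off drug, enter the primary analysis; the Day 176 run shows how much they matter.
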